The protocol, informed consent form(s), recruitment materials, and all participant materials will be submitted to the Institutional Review Board (IRB)/Independent Ethics Committee (IEC) for review and approval. Approval of both the protocol and the consent form must be obtained before any participant is enrolled. Any amendment to the protocol will require review and approval by the IRB/IEC before the changes are implemented to the study. In addition, all changes to the consent form will be IRB/IEC-approved; a determination will be made regarding whether a new consent needs to be obtained from participants who provided consent, using a previously approved consent form.

PROTOCOL SUMMARY

1.1 SYNOPSIS

Title: A Phase 1/2 Open Label, Multicenter Study to Assess the Safety,

Tolerability, Pharmacokinetics, and Anti-Tumor Activity of ZN-c5 Alone and in Combination with Palbociclib in Subjects with Estrogen-Receptor Positive, Human Epidermal Growth Factor Receptor-2 Negative Advanced Breast

Cancer

Study Description: The study has 5 components:

Phase 1

- Monotherapy Dose Escalation
- Monotherapy Expansion
- Combination Dose Escalation

Phase 2

- Monotherapy Phase 2
- Combination Phase 2

Objectives: Primary Objectives:

Phase 1

- Monotherapy Dose Escalation: Determine a maximum tolerated dose (MTD) or recommended Phase 2 dose (RP2D) for ZN-c5 as a monotherapy
- Monotherapy Expansion: Investigate the safety and tolerability of ZN-c5 as a monotherapy in subjects with Estrogen Receptor (ER) positive, Human Epidermal Growth Factor Receptor-2 (HER2) negative advanced breast cancer
- Combination Dose Escalation: Determine an MTD or RP2D for ZN-c5 when administered in combination with palbociclib

Phase 2

- Monotherapy Phase 2: Determine preliminary anti-tumor efficacy (Clinical Benefit Rate [CBR]) for ZN-c5 as a monotherapy
- Combination Phase 2: Determine preliminary anti-tumor efficacy
 (CBR) for ZN-c5 when administered in combination with palbociclib

Secondary Objectives:

- Monotherapy Dose Escalation and Monotherapy Phase 2:
 Investigate the safety and tolerability of ZN-c5 as a monotherapy in subjects with ER positive, HER2 negative advanced breast cancer
- Combination Dose Escalation and Combination Phase 2: Investigate
 the safety and tolerability of ZN-c5 in combination with palbociclib
 in subjects with ER positive, HER2 negative advanced breast cancer

- Monotherapy Expansion Phase 1: Investigate the preliminary anti-tumor efficacy (CBR) for ZN-c5 as a monotherapy
- All Cohorts: Assess preliminary efficacy of ZN-c5 alone and in combination with palbociclib by Objective Response Rate (ORR), CBR, Duration of Response (DOR), Progression-Free Survival (PFS) and Overall Survival (OS) using Response Evaluation Criteria in Solid Tumors (RECIST v.1.1) as assessed by investigators
- Monotherapy Dose Escalation and Monotherapy Expansion Phase 1 and Monotherapy Phase 2: Characterize the pharmacokinetics (PK) of ZN-c5 (and its potential metabolites as applicable) when given as oral monotherapy
- Combination Dose Escalation and Combination Phase 2: Characterize the PK of ZN-c5 (and its potential metabolites as applicable) when given in combination with palbociclib
- Combination Dose Escalation and Combination Phase 2:
 Characterize the PK of palbociclib when given in combination with ZN-c5

Tertiary/Exploratory Objectives (All Cohorts):

- Evaluate pharmacodynamic and prognostic biomarkers associated with disease prognosis and/or likelihood of response to ZN-c5
- Assess the effect of ZN-c5 on tumor's ability to bind estradiol as measured by uptake of ¹⁸F-fluoroestradiol (FES) Positron Emission Tomography (PET)

Endpoints:

Primary Endpoints:

- Monotherapy Dose Escalation and Combination Dose Escalation:
 Observed Dose Limiting Toxicities
- Monotherapy Expansion: Safety and tolerability as measured by incidence of treatment-emergent adverse events (TEAEs) and lab abnormalities
- Monotherapy Phase 2 and Combination Phase 2: CBR (CR [+ PR] + SD ≥ 24 weeks). PR will only be included for patients with measurable disease.

Secondary Endpoints:

- All Cohorts: Safety and tolerability as measured by incidence of treatment-emergent AEs and lab abnormalities
- Monotherapy Expansion: CBR (CR [+ PR] + SD ≥ 24 weeks). PR will
 only be included for patients with measurable disease.

- All Cohorts: Tumor response including ORR, DOR, CBR, PFS using Response Evaluation Criteria in Solid Tumors (RECIST v.1.1) as assessed by Investigators, and OS
- All Cohorts: ZN-c5 (and its potential metabolites as applicable) and palbociclib (if applicable) plasma pharmacokinetic (PK) parameters (including C_{max}, T_{max}, AUC_{last}, t_½ and C_{tau}, as applicable)

Tertiary/Exploratory Endpoints (All Cohorts):

- Pharmacodynamic or prognostic markers (including but not limited to estrogen receptor degradation, Ki-67, RNA-Seq, 4βhydroxycholesterol/cholesterol and ESR1 mutations)
- FES-PET Scan (18F-fluoroestradiol radiotracer)

Study Population:

Phase 1 Monotherapy Dose Escalation and Combination Dose Escalation: Adult subjects with advanced ER+/HER2-negative advanced breast cancer who are refractory to or intolerant of established therapy(ies) known to provide clinical benefit for their malignancy.

Phase 1 Monotherapy Expansion: Adult subjects with advanced ER+/HER2-negative advanced breast cancer who have received up to 2 prior lines of endocrine-based therapy for advanced/metastatic breast cancer.

Phase 2 Monotherapy: Adult subjects with advanced ER+/HER2-negative breast cancer who have received 1 or 2 prior lines of endocrine-based therapy for advanced/metastatic breast cancer.

Phase 2 Combination: Adult subjects with advanced ER+/HER2-negative breast cancer who have received up to 1 prior line of endocrine-based therapy for advanced/metastatic breast cancer.

Phase: 1/2

Estimated No. of Sites: Approximately 60 centers globally, including the US

Estimated No. of Subjects:

Phase 1 Monotherapy Dose Escalation: Approximately 36 subjects Phase 1 Monotherapy Expansion: Approximately 45 subjects Phase 1 Combination Dose Escalation: Approximately 40 subjects

Phase 2 Monotherapy: Approximately 225 subjects Phase 2 Combination: Approximately 112 subjects ESTIMATED TOTAL: Approximately 458 subjects

Study Intervention: ZN-c5

Palbociclib (IBRANCE®); Pfizer, Inc.

Overall Study Design: Phase 1/2 trial of ZN-c5 both as monotherapy and in combination with

palbociclib.

The study consists of **5 components**:

Phase 1 Monotherapy Dose Escalation and Phase 1 Monotherapy

Expansion: Single agent ZN-c5 will be evaluated at sequentially escalating doses starting with 50 mg and up to 1200 mg administered orally, once daily

(alternatively, this total daily dose may be divided by 2 and administered BID [every 12 hours]), using a 28-day cycle (Dose Escalation). During or on completion of the Dose Escalation, additional patients may be enrolled onto one or more dose levels for the Monotherapy Expansion portion of the study. The decision to expand will be based on the PK, safety and available biomarker data.

Phase 2 Monotherapy: ZN-c5 will be administered at the single agent RP2D and schedule. This Monotherapy Phase 2 portion will follow a randomized, parallel cohort, non-comparative (estimation) design and up to 3 dose levels of ZN-c5 will be assessed.

Phase 1 Combination Dose Escalation and Phase 2 Combination: In Phase 1, ZN-c5, starting at a dose level deemed well-tolerated (as determined from the Monotherapy Dose Escalation) will be evaluated in combination with palbociclib in ascending dose cohorts to assess the safety and determine the MTD or RP2D. ZN-c5 will be administered orally once daily (alternatively, this total daily dose may be divided by 2 and administered BID [every 12 hours]), on a 28-day treatment cycle. In Phase 2 Combination, ZN-c5 will be dosed at the RP2D and potentially at a lower dose level in combination with palbociclib. The lower ZN-c5 dose will be selected based on available safety, PK and biomarker data. The dose and schedule of palbociclib will be the Regulatory Authority's approved dose of 125 mg taken orally once daily for 21 consecutive days followed by 7 days off treatment (1 cycle of treatment = 28 days) for both the Phase 1 Combination Dose Escalation and Phase 2 components of the study. During the Dose Escalation, additional patients may be enrolled onto one or more dose levels (backfill). The Combination Phase 2 will follow a randomized, parallel group, non-comparative design, assuming both the RP2D and the lower dose are investigated, or a single dose cohort design, if only the RP2D is investigated. Each dose cohort will follow a Simon 2-stage design.

Study Duration: 60 months

[figure not shown]
Participant Duration: Treatment will continue in the absence of disease progression,

unacceptable toxicity, withdrawal of consent, or other reason (specified in

Section 7.2).

[figure not shown]
1.2 SCHEMA

Figure 1 ZN-c5-001 Phase 1 Monotherapy Dose Escalation, Expansion and Phase 2

The dose in mg is the total dose/day

Figure 2 ZN-c5-001 Phase 1 Combination with Palbociclib Dose Escalation and Phase 2

^{*} Decision on which ZN-c5 dose to start the expansion will depend on the PK profile, safety and any available biomarker data

Palbociclib is dosed at 125 mg/day taken orally once daily for 21 consecutive days, followed by 7 days off treatment to comprise a complete cycle of 28 days.

^{**} More than 3 ZN-c5 dose levels may be assessed based on the Monotherapy Dose Escalation

1.3 SCHEDULE OF ACTIVITIES

Table 1: Study Procedures Table

Study Phase	Screening		(28	Cycle 1	cle)			'ycles ≥ 2 -day cycle)	ЕОТ	30-day Safety Follow- up	Disease Assess ment Follow- up ²¹ (every 12 weeks)	Survival Follow- up ²² (every 12 weeks)
Cycle Day	Day -28	Day 1	Day 2	Day 8	Day 15	Day 16	Day 1	[Day 15* Cycle 2 Combination only]				
Window (days)	-28 to -1			± 1	± 2		[± 4 ²³]	[± 2]	± 7	± 7	± 7	± 14
Informed Consent	Х											
Medical and Medication History ¹	х											
Physical Examination ²	х	х		х	х		х	[X]	Х	Х		
ECOG Performance Status	Х	х					х	[X]	Х	Х		
Vital Signs ³	Х	Х		Х	Х		Х	[X]	Х	Х		
Triplicate 12- lead ECG ⁴	Х	х	[X]		Х	[X]	[X]		Х			
Adverse events/ Concomitant medications ⁵	[X]	х	[X]	х	х	[X]	х	[X]	х	х		
Enrollment	Х											
Hematology	X ⁷	Х		Х	Х		Х	[X]	Х	Х		
Chemistry	X ⁷	Х		Х	Х		Х	[X]	Х	Х		
Coagulation ⁸	X ⁷								Х			
Full Lipid Panel ⁹		[X]					[X]					
Urinalysis ¹⁰	X ⁷								Х			
Pregnancy Test ¹¹	Х	Х					х		Х	Х		
PK ¹²		[X]	[X]	[X]	[X]	[X]	[X]					

Study Phase	Screening		(28	Cycle 1 3-day cyc				'ycles ≥ 2 -day cycle)	ЕОТ	30-day Safety Follow- up	Disease Assess ment Follow- up ²¹ (every 12 weeks)	Survival Follow- up ²² (every 12 weeks)
Cycle Day	Day -28	Day 1	Day 2	Day 8	Day 15	Day 16	Day 1	[Day 15* Cycle 2 Combination only]				
Window (days)	-28 to -1			± 1	± 2		[± 4 ²³]	[± 2]	± 7	± 7	± 7	± 14
ZN-c5 pharmaco- dynamic and exploratory biomarkers in blood ¹³		х					х		[X]		[X]	
Tumor Biopsy ¹⁴	[X]						[X]		[X]		[X]	
ESR1 Mutation ¹⁵		х					х		[X]		[X]	
CT/MRI ¹⁶	Х						Х		Х		[X]	
4β- hydroxycholest erol / cholesterol ¹⁷		х			х		х					
FES-PET ¹⁸	[X]						[X]					
ZN-c5 oral dosing ¹⁹						Х						
Palbociclib oral dosing (Combo only) ²⁰			[X]									
Subject Dosing Diary Accountability and/or Dispensing ⁶		х					х		Х			
LTFU ²²												[X]

Notes: X = Required; [X] = Only applicable as per footnote as indicated by the Assessment

Cycle 1 Day 1 safety lab samples, physical examination, ECOG status and pregnancy test may be assessed up to 3 days prior to the Day 1 visit. On subsequent visits throughout the study, these procedures/assessments are allowed to be performed within 1 day prior to the planned visit.

Cycle 1 Days 2 and 16 are only required for subjects participating in the Phase 1 parts of the protocol.

*Cycle 2 Day 15 visit – only for subjects participating in Combination Therapy (Combination Dose Escalation and Phase 2)

1. Medical history includes significant past medical events (e.g., prior hospitalizations or surgeries), a review of the disease under study, prior anti-cancer therapies, and any concurrent medical illnesses.

- 2. Screening and End of Treatment Physical Examinations (PE) will be a complete PE. Beginning at C1D1, a modified physical examination may be performed. Weight (without shoes) should be measured at each PE. Height (without shoes) is measured at Screening only.
- 3. C1D1 Vital Signs will be taken within 15 min pre-ZN-c5 dose and 2 and 4 hours post-dose (Phase 1) or pre-dose and 2 hours post-dose (Phase 2); vital signs will be taken pre-dose only at all subsequent visits. Oxygen saturation will be tested with a pulse oximeter.
- 4. Resting, semi recumbent triplicate ECGs will be collected at any time during Screening window, Day 1 of every other cycle (alternating cycles) starting with Cycle 2 (at pre-dose), and at EOT. In Phase 1, triplicate ECGs will be collected on C1D1 and C1D15 at pre-dose, 8 hours, and 24 hours post-dose (pre-dose on C1D2 and C1D16). In Phase 2, triplicate ECGs will be collected on C1D1 and C1D15 at pre-dose and 2 hours post-dose. ECGs should preferably be collected prior to PK (or any other blood draw) if they are to be collected at the same nominal time point. ECGs should be collected over a 5-minute window at each time point.
- 5. AEs will be assessed using NCI CTCAE (v 4.03) criteria. Subjects will also return to clinic at 30-days (± 7 days) post last IP dose (but prior to initiation of subsequent breast cancer therapy) to assess AEs and SAEs. At Screening, all medications taken up to 30 days prior to Screening will be documented in the eCRF.
- 6. Subjects will be given a Subject Diary on which they will record dates/times of study drug administration. Compliance with study drug(s) will be assessed and reviewed during visits.
- 7. Screening chemistry, hematology, coagulation, and urinalysis should be collected within 7 days of C1D1.
- 8. Coagulation assessment includes PT/INR, aPTT.
- 9. A non-fasting full lipid panel will be performed on C1D1, C3D1 (coinciding with the first on-study tumor assessment after 8 weeks) and C7D1 (6 months into the study). This will not be collected in the Monotherapy Phase 2.
- 10. Urinalysis assessment includes visual inspection, microscopic examination, and dipstick test for pH, protein, glucose, WBC, bilirubin, and blood.
- 11. Serum pregnancy testing will be conducted at Screening (within ≤ 7 days of C1D1). Serum or urine pregnancy tests thereafter will be done on Day 1 of every cycle for all premenopausal and perimenopausal female subjects of childbearing potential, including EOT and the Safety Follow-up Visit.
- 12. Plasma samples for PK analysis of ZN-c5 (having been administered without food [at least 1 hour before and 2 hours after a meal]) and of palbociclib (having been administered with food) will be collected relative to ingestion of each drug as per Table 6 and Table 7. Regarding the PK sampling for ZN-c5 if administered twice daily (BID), a sample at 12 hours post morning dose and immediately preceding the second daily dose may also be collected (optional). Note: If the optional, On-Treatment tumor biopsy is performed, an additional PK sample should be collected at that time.
- 13. Whole blood, serum and/or plasma will be collected for exploratory biomarkers at C1D1, C2D1, and at time of disease progression.
- 14. Tumor biopsy: At baseline, *de novo* biopsy of any amenable site of disease (at investigator's discretion). Additional tumor biopsy at C2D1 or any time beyond may also be obtained. The on-treatment biopsy should be obtained 2 4 hours after the subject has taken the ZN-c5 dose that day. Subjects will also have the option to undergo a biopsy of a lesion at the time of disease progression. Samples will be collected, labelled, stored and shipped as detailed in the laboratory manual. Any residual tumor remaining after analysis may be used for exploratory research into factors that may influence development of breast cancer and/or response to ZN-c5. All tumor biopsies are optional for all subjects participating during the study. Biopsies must not be taken from target lesions used to assess anti-tumor efficacy, if possible. If sufficient tumor material is available, part of the tumor biopsy at C2D1 will be used for determination of ZN-c5 tissue concentration. If a biopsy is obtained on C2D1 or beyond, a plasma PK sample should also be collected, as close as possible, within 2 hours prior to the biopsy.
- 15. A blood sample for the assessment of ESR1 mutations will be drawn at C1D1, C2D1, and at time of progression.
- 16. Tumor evaluation by CT/MRI or applicable scan will be performed during Screening (within 28 days of Cycle 1 Day 1) and every 8 weeks (± 7 days) after C1D1 for the first 24 weeks. After 24 weeks, scans may be performed every 12 weeks (± 7 days). The same radiographic procedure used to define measurable lesions must be used throughout the study for each subject. Applicable scans to be done at EOT visit if not done within the previous 4 weeks.
- 17. Plasma samples for 4β -hydroxycholesterol and cholesterol will be collected pre-dose on C1D1, C1D15, and pre-dose on Day 1 of Cycles 2-4 of the Monotherapy Dose Escalation and Expansion.
- 18. A FES-PET scan (optional) should be conducted at Screening and at least after 1 month of treatment (preferably within the first 2 months, in Cycle 2).
- 19. Beginning on C1D1, subjects will take ZN-c5 once daily (alternatively, this total daily dose may be divided by 2 and administered BID [every 12 hours]). ZN-c5 dosing and administration as per assigned cohort (see Section 6.1.2.1).
- 20. In Phase 1, beginning on C1D1, subjects in the combination treatment cohorts will take palbociclib at the label indicated dose of 125 mg orally once daily (2 hours after the ZN-c5 dose was taken) for 21 consecutive days followed by 7 days off treatment (1 cycle of treatment = 28 days) (see Section 6.1.2.2). In Phase 2, subjects in the combination treatment cohorts will take palbociclib at the label indicated dose of 125 mg orally once daily (at the same time the ZN-c5 dose is taken) for

- 21 consecutive days followed by 7 days off treatment (1 cycle of treatment = 28 days).21. Disease Assessment Follow-up Visit: Subjects without progression of disease (PD) at the time of study drug discontinuation will continue to undergo disease evaluations every 12 weeks \pm 7 days until confirmation of PD, initiation of the first subsequent cancer therapy, withdrawal of consent, death, loss to follow-up, or until the study is terminated. Once a subject has confirmation of PD or has initiated subsequent cancer therapy, whichever occurs first, disease follow-up will discontinue.
- 22. Long-term Follow-up (LTFU) Subjects will be contacted every 3 months (phone or medical records) for survival status and collection of subsequent breast cancer treatments.
- 23. In the Combination Dose Escalation and Combination Phase 2 with palbociclib, the window for the Day 1 visit for subsequent cycles is only + 4 days, since there must always be at least a full 7-day off treatment recovery period for palbociclib before starting the next 21-day dosing cycle.

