6.1.5 COMBINATION DOSE ESCALATION

Dose escalation in combination with palbociclib will be initiated at a ZN-c5 dose that is deemed well-tolerated in the Monotherapy Dose Escalation and will proceed with higher ZN-c5 doses, as tolerated in the Monotherapy Dose Escalation, based on standard rules of 3+3 design in order to define an MTD/RP2D for ZN-c5 in combination with palbociclib (Section 6.1.3). The total number of patients will depend upon the number of dose escalations necessary, but it is estimated to be approximately 40 subjects (including alternate dosing schedules, e.g., BID, and possible backfill).

Dose levels and schedule will follow the dose levels and schedule per the Monotherapy Dose Escalation.

Additional subjects can be enrolled at a lower dose level already deemed tolerated (backfill). At least 6 subjects will be treated at the MTD/RP2D.

The subjects treated in the Combination Dose Escalation can possibly count towards the futility assessment stage accrual (Section 9.2.4, Combination Phase 2).

The dose of palbociclib used in the combination phases of the study will be the Regulatory Authority approved dose and schedule (125 mg PO QD \times 21 days, followed by 7 days off treatment).

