8.2.2 PHARMACOKINETIC, PHARMACODYNAMIC, & CORRELATIVE SAMPLES

8.2.2.1 PHARMACOKINETIC SAMPLES

Details of sample preparation and procedures for transfer of samples to the central laboratory are provided in the Laboratory Manual.

Plasma samples for ZN-c5 (and its potential metabolites as applicable) (± palbociclib) will be collected as described in Table 5.

b Includes direct bilirubin

Table 5: Pharmacokinetic Sampling per Study Component

Study Component	N subjects and type of PK	PK Time Points
Monotherapy Dose Escalation	therapy Dose Escalation Full ZN-c5 PK in all subjects	
Monotherapy Expansion – at each dose level assessed	Full ZN-c5 PK in approximately 6 – 12 subjects in total, subjects from the Monotherapy Dose Escalation treated at the same dose level and with evaluable PK data included	Table 6 (Monotherapy)
	Abbreviated ZN-c5 PK schedule for the remaining subjects (optional)	Table 7
Monotherapy Phase 2	Abbreviated ZN-c5 PK schedule in all subjects (optional)	Table 7
Combination Dose Escalation	Full ZN-c5 + palbociclib PK in all subjects	Table 6 (Combination Therapy)
Combination Phase 2 – Stage 1 – at each dose level assessed	Full ZN-c5 + palbociclib PK in approximately 6 – 12 subjects in total, subjects from the Combination Dose Escalation treated at the same dose level and with evaluable PK data included	Table 6 (Combination Therapy)
	Abbreviated ZN-c5 + palbociclib PK schedule for the remaining subjects (optional)	Table 7
Combination Phase 2 – Stage 2	Abbreviated ZN-c5 + palbociclib PK schedule in all subjects (optional) Table 7	

The decision to switch from a full PK schedule to an abbreviated PK schedule (population PK) will depend on the variability of the ZN-c5 PK parameters observed in the subjects with full PK. If required, more subjects in the Monotherapy Phase 2 or in the Combination Phase 2 (Stage 2) will continue to be assessed with full PK.

In the combination cohorts, on PK days, palbociclib should be taken with food 2 hours after the ZN-c5 dose.

Table 6: Full Pharmacokinetic Sampling Time Points

Day on Study	Time (hr)	Monotherapy	Combination Therapy	
		ZN-c5	ZN-c5	Palbociclib
Cycle 1 Day 1 and 15	T=0	PK (pre-dose, within 0.5 hrs)	PK (pre-dose, within 0.5 hrs)	NA
		Dose (fasted)	Dose (fasted)	NA
	0.5	PK	PK	NA
	1	PK	PK	NA
	2	PK	PK (prior to Palbociclib dosing)	PK (pre-dose, within 0.5 hrs) Dose (with food)
	2.5	NA	NA	PK (0.5-hr)
	3	NA NA	NA NA	PK (0.3-111)
	4	PK	PK	PK (1-111)
	6	PK	PK	PK (4-hr)
	8	PK	PK	PK (6-hr)

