	10	NA	NA	PK (8-hr)
Cycle 1	24	PK	PK	NA
Day 2 and 16	26	NA	NA	PK (24-hr)
Cycle 1 Day 8		PK (pre-dose, within 0.5 hrs)	PK (pre-dose, within 0.5 hrs)	РК
Cycle 2 Day 1		PK (pre-dose, within 0.5 hrs)	PK (pre-dose, within 0.5 hrs)	NA
Cycle 3 Day 1		PK (pre-dose, within 0.5 hrs)	PK (pre-dose, within 0.5 hrs)	NA
Cycle 4 Day 1		PK (pre-dose, within 0.5 hrs)	PK (pre-dose, within 0.5 hrs)	NA
NA= not applic	able	,	,	

In case the dosing schedule is changed to BID dosing, an additional PK time point at 12 hours post ZN-c5 dosing will be drawn (optional).

Table 7: Abbreviated Pharmacokinetic Sampling Time Points

Day of Study	Collection Time Points (and Allowable Windows)	ZN-c5	Palbociclib*
Cycle 1 Day	Pre-dose (within 0.5 hour prior to ZN-c5 administration)	Х	Х
15	2-hours (± 10 min) post ZN-c5 administration	Х	Х
	4-hours (± 1 hour) post ZN-c5 administration	Χ	Х
*in the combination parts of the study			

All efforts will be made to obtain the PK samples at the exact nominal time relative to dosing, however, samples obtained within 10% of nominal time from dosing are acceptable for up to and including the

12-hour time points. The 24-hour time points should be drawn within \pm 1 hour. A protocol deviation only applies if a PK time point is missed.

If the optional On-Treatment tumor biopsy is performed, an additional PK sample should be collected at that time, regardless if tissue was obtained for ZN-c5 tissue concentration.

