For the purpose of calculating AUC, all missing values will be treated as missing in the PK analysis and excluded from analysis except when they occur at pre-dose (of Day 1), where they will be set to 0. Missing pre-dose values for all other days will be handled on a case-by-case basis and may be imputed using the C_{trough} value for that corresponding dosing interval. If C_{trough} value is missing, the missing pre-dose will be imputed using the lowest concentration value observed for that corresponding dosing interval, if warranted.

All AUCs including partial AUCs (AUC₀₋₈, AUC₀₋₁₂, AUC₀₋₂₄, and AUC_{tau}) will be calculated using the linear trapezoidal method and actual elapsed time values. AUC₀₋₂₄ for the BID dosing will be determined by estimating $2 \times$ AUC₀₋₁₂ for Cycle 1 Day 15. If no PK sample was collected at the 12 or 24 hour post dose for either the BID or QD dosing regimen, one of two approaches will be taken to allow for the determination of AUC₀₋₈, AUC₀₋₁₂, AUC₀₋₂₄ or AUC_{tau}:

- For Cycle 1 Day 1, the 12 or 24 hour post-dose sample will be calculated via an extrapolation method using Phoenix® WinNonlin® standard calculations. If no lambda z is estimated, AUC₀₋₈, AUC₀₋₁₂ or AUC₀₋₂₄ will not be estimated. Moreover, the adjusted r^2 value must be ≥ 0.8 and AUC_{extr} must be <20% for AUC₀₋₈, AUC₀₋₁₂, and AUC₀₋₂₄ to be estimated by extrapolation.
- For Cycle 1 Day 15, the 12 or 24 hour post-dose sample will be imputed using the pre-dose concentration or the minimum observed concentration within that BID or QD dosing interval (if the pre-dose concentration is missing) to obtain the AUC_{tau}.

CL/F on Day 1 will be calculated as Dose (D)/AUC₀₋₁₂ or AUC₀₋₂₄ and CL_{ss}/F on Day 15 will be calculated as Dose (D)/AUC_{tau} (where tau = 12 or 24 hours).

V/F on Day 1 will be calculated as D/(λ * AUC₀₋₁₂ or AUC₀₋₂₄) and V_{z,ss}/F on Day 15 will be calculated as D/(λ * AUC_{tau}) (where tau = 12 or 24 hours).

C_{ave} will be calculated as AUC_{tau}/12 or AUC_{tau}/24 (where tau = 12 or 24 hours).

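### The Phase 2 visit note conflicts with the full-PK sampling in Tables 5 and 6, and the SAP does not limit its Day 15 AUC imputation to full-schedule subjects

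*Protocol*

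**What the plan says.** **Visits.** Under protocol Table 1 (section 1.3), and again under SAP Table 2 (section 3.7), the plan states: "Cycle 1 Days 2 and 16 are only required for subjects participating in the Phase 1 parts of the protocol".

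**Full schedule.** Protocol Table 5 (section 8.2.2.1) specifies, for each dose level in Combination Phase 2 Stage 1, "Full ZN-c5 + palbociclib PK in approximately 6 – 12 subjects in total", with "subjects from the Combination Dose Escalation treated at the same dose level and with evaluable PK data included". These subjects follow Table 6, which takes the 24 h ZN-c5 sample and the 26 h sample (24 h after palbociclib) on Cycle 1 Days 2 and 16. Without those days the last samples are at 8 h for ZN-c5 and 10 h for palbociclib, that is 8 h after the palbociclib dose. Section 8.2.2.1 also allows full PK to continue in Monotherapy Phase 2 or Combination Stage 2 if needed.

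**Abbreviated schedule.** The remaining Stage 1 subjects, Stage 2, and Monotherapy Phase 2 (up to 225 subjects) have the optional Table 7 schedule: Cycle 1 Day 15 only, at pre-dose, 2 h and 4 h. Section 8.2.2.1 labels it population PK.

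**Analysis.** SAP 6.5.6 lists only the full schedule. SAP 6.7.3 uses the linear trapezoid and covers the case of an absent 12 h or 24 h sample. On Day 1 the value is extrapolated only if a terminal slope is estimated, adjusted r² is at least 0.8 and the extrapolated AUC is below 20%. On Day 15: "For Cycle 1 Day 15, the 12 or 24 hour post-dose sample will be imputed using the pre-dose concentration", or the interval minimum if pre-dose is missing. Half-life needs at least three terminal points excluding Cmax, and a span of at least 2 to enter the summaries.

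**The concern.** There are two separate gaps.

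First, a site that follows the visit note would not bring a Phase 2 full-PK subject back on Day 2 or Day 16. Nothing else in the schedule would do so, because the Phase 2 ECGs stop at 2 h post-dose. The SAP's own quality rules would then remove most of what the full schedule was meant to provide beyond 8 h.

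Second, every once-daily Table 7 subject lacks a 24 h sample by design and so meets the trigger of the Day 15 imputation rule. The SAP includes no population PK analysis for these data and no statement that they stay out of the noncompartmental analysis. Applied as written, the rule would place three-sample AUCtau values beside full-profile values from Phase 1.

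Plasma PK, including AUClast, half-life and Ctau, is a secondary endpoint for all cohorts. Monotherapy Phase 2 is there to settle the dose for further development, so its exposure figures should be comparable with those from Phase 1.

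**Working it through.** The plan states no figure on this point that could be reproduced. The documents give no ZN-c5 half-life or absorption rate, so every size below is conditional on an assumption.

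**1. How many Phase 2 subjects need Days 2 and 16?** The Table 5 target is 6-12 per dose level, minus same-dose Phase 1 subjects with evaluable PK.
- RP2D: protocol 6.1.5 says "At least 6 subjects will be treated at the MTD/RP2D". With 6 evaluable, 6 − 6 = 0 to 12 − 6 = 6 more.
- A lower dose with 3 to 6 Phase 1 subjects: 6 − 6 = 0 to 12 − 3 = 9 more.
- A dose not studied in Phase 1: up to 12.

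**2. Full schedule, last ZN-c5 sample at 8 h, Day 1, once daily.** In the simplest exponential limit the extrapolated fraction is exp(−8k), with k = ln 2 / t½. The SAP limit needs exp(−8k) < 0.20, so t½ < 8 × ln 2 / ln 5 = 3.4 h. With absorption included (one-compartment oral model, Tmax 1-3 h) the limit lies at about 2.2-3.3 h. For t½ of 4-24 h the extrapolated share is 27-81%. AUC0-24 is then not estimated, and the once-daily accumulation ratio, which divides by it, is lost too.

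**3. Half-life span rule.** Span = interval used / t½, and must be at least 2.

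| Terminal points | Interval | Largest t½ that passes |
|---|---|---|
| 4-8 h | 4 h | 2 h |
| 1-8 h | 7 h | 3.5 h |
| 4-24 h (with the 24 h sample) | 20 h | 10 h |

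**4. Full schedule, Day 15.** At steady state on once-daily dosing the pre-dose concentration equals the 24 h concentration. In the model, AUCtau is the same whether the 24 h value is observed or imputed (both 0.1-22.5% above true over t½ 2-36 h, because of the linear trapezoid from 8 to 24 h). The missing visit therefore does no harm to this parameter.

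**5. Abbreviated schedule, Day 15, once daily, rule applied literally.** The trapezoid uses 0, 2, 4 and 24 h with C24 set to pre-dose. Example with ka = 1 per h and t½ = 4 h (k = 0.1733), in units of dose/volume:
- Concentrations at 0, 2, 4 and 24 h: 0.019, 0.705, 0.592, 0.019.
- Segments: (0.019 + 0.705)/2 × 2 = 0.724; (0.705 + 0.592)/2 × 2 = 1.297; (0.592 + 0.019)/2 × 20 = 6.11. Sum 8.14 (unrounded concentrations).
- True AUCtau = 1/k = 5.77. Ratio 8.14/5.77 = 1.41, or +41%.
- The full Table 6 times give 6.66 (+15.5%), so the sparse value exceeds the full-schedule value by 8.14/6.66 = 1.22, or +22%.

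Across Tmax 1-3 h:

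| Assumed t½ | Sparse AUCtau vs true | Sparse vs full schedule |
|---|---|---|
| 4 h | +32% to +41% | +16% to +22% |
| 8 h | +10% to +13% | +3% to +6% |
| 12 h | about +4% to +6% | about 0 to +2% |
| 24 h | within about 1% | within about 1% |

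Over a wider grid (ka 0.5-2 per h, t½ 2-36 h) the error against true ranges from −1.5% to +74%.

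**6. Abbreviated half-life.** There are at most two measured post-dose points against a minimum of three, so half-life is not estimable.

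**The case against.** The strongest case on the other side has five parts.

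- *The note is not a ban.* It says when the visits are required. The PK cells for Days 2 and 16 are conditional on footnote 12, under which samples "will be collected relative to ingestion of each drug as per Table 6 and Table 7". A site that knows its subject is on full PK is led to the 24 h draw. This stands as a limit on how often samples would be lost, but two instructions on the same page still disagree.
- *Phase 1 subjects may fill the quota.* This stands. At the RP2D the minimum may already be met.
- *The SAP never says it applies the rule to Table 7 data.* True. The protocol calls that schedule population PK, and the PK Analysis Set asks for interpretable results for the parameters of interest, so an analyst could leave those subjects out. The point rests on the absence of a restriction, not on a stated intention.
- *PK parameters are listed only as applicable, and much survives.* On the full schedule without the 24 h sample, Day 15 AUCtau, Cmax, Tmax and the troughs are intact. AUClast can still be computed, though it then ends at 8 h. For twice-daily ZN-c5 the accumulation ratio may use AUC0-8, and tau is 12 h, so the 24 h visit is not the issue for its AUCtau.
- *Practical reach.* The SAP treats Combination Phase 2 as a part that may not be executed, and PK is not among the data collected after the May 2022 cut-off. This limits what a schedule amendment can still achieve. It does not affect the SAP clarification.

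A reader might go further and infer that Phase 2 AUC and half-life as a whole will be missing or biased, or that imputing the pre-dose value is itself the source of bias. The documents support neither. Half-life would be missing or left out of the summaries, not biased. The imputed value is sound at steady state. The error in sparse data comes from the straight line between 4 h and 24 h.

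**Conclusion.** The concern holds in a limited form. The visit note and Tables 5 and 6 contradict each other for any Combination Phase 2 Stage 1 subject on full PK: perhaps none at the RP2D, at most 12 at a dose new to Phase 2. For those subjects, following the note costs once-daily Day 1 AUC0-24 and accumulation unless half-life is below about 3 h. Half-life from the 4-8 h points fails the span rule unless it is 2 h or less.

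The SAP gap covers more subjects, because it also reaches Monotherapy Phase 2. Its size depends entirely on a half-life the documents do not give: material at 4 h, modest at 8 h, negligible at 24 h, under one-compartment kinetics and once-daily dosing.

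The textual conflict is certain; the numerical consequence is conditional. No sample size, CBR analysis or futility decision depends on it, and the schedule part matters only if Combination Phase 2 is run. It should be corrected, but it does not threaten the trial's main conclusions.

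**What to change.** 1. **Schedule notes (protocol Table 1 and SAP Table 2).** Reconcile them with Tables 5 and 6. One way is to state that Cycle 1 Days 2 and 16 apply in Phase 1 and to Phase 2 subjects assigned to full PK under Table 6. If the sponsor does not want these visits in Phase 2, Table 5 should instead stop assigning Table 6 there.
2. **SAP 6.7.3.** Restrict noncompartmental AUCtau and half-life, and the 12/24 h imputation, to subjects sampled on the Table 6 schedule. Use Table 7 data for pre-dose, 2 h and 4 h concentration summaries and for the population PK purpose named in protocol 8.2.2.1.

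**Cost.** One sentence in each place, and no samples beyond those Table 6 already plans. Under the first option, the few remaining Phase 2 full-PK subjects attend two more visits, which Table 6 already implies. No individual AUCtau would be reported for abbreviated-schedule subjects.
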